8.1.3. Other Stopping Criteria

Dosing will be stopped for any individual participant in case of SAEs and in case of any AEs which in the opinion of the investigator might jeopardise the health of the trial participant.

Additionally, dosing will be stopped and the study will be put on halt if any of the below scenarios occurred. If following an internal safety review the Sponsor deems it appropriate to restart the trial, this can be done following approval of a substantial amendment:

Two (2) or more subjects, within a dose-level, receiving study treatment experience grade 3 respiratory adverse event that are deemed possibly or probably related to study drug by the investigator.

Two (2) or more subjects, within a dose-level, receiving study treatment experience a grade 3 hematologic adverse event that are deemed possibly or probably related to study drug by the investigator.

Two (2) or more subjects, within a dose-level, receiving study treatment experience severe hypersensitivity related adverse event that are deemed possibly or probably related to study drug by the investigator.

Two (2) or more subjects, within a dose-level, receiving study treatment experience a grade 3 vital signs (heart rate and/ or blood pressure) adverse event that are deemed possibly or probably related to study drug by the investigator.

One (1) or more subjects receiving study treatment experience anaphylaxis that is deemed possibly or probably related to study drug by the investigator.

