8.2. Withdrawal from the Study

- A participant may withdraw from the study at any time at his/her own request, or may be withdrawn at any time at the discretion of the investigator for safety, behavioral, compliance or administrative reasons.
- If the participant withdraws consent for disclosure of future information, the sponsor may retain and continue to use any data collected before such a withdrawal of consent.
- If a participant withdraws from the study, he/she may request destruction of any samples taken and not tested, and the investigator must document this in the site study records.
- Refer to the SoA (Section 2) for data to be collected at follow-up and for any further evaluations that need to be completed.
- Participants will have to be followed up for safety reasons as deemed necessary by the Investigator and should be encouraged to return for a follow-up visit as specified in the SoA (Section 2). If this is not possible, procedures specified for the follow-up visit can be performed at the last visit that the participant attends.

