9. STUDY ASSESSMENTS AND PROCEDURES

- Study procedures and their timing are summarized in the SoA (Section 2).
- Protocol waivers or exemptions are not allowed
- Immediate safety concerns should be discussed with the sponsor immediately upon occurrence or awareness to determine if the participant should continue or discontinue study treatment.
- Adherence to the study design requirements, including those specified in the SoA (Section 2), is essential and required for study conduct.
- All screening evaluations must be completed and reviewed to confirm that potential
 participants meet all eligibility criteria. The investigator will maintain a screening
 log to record details of all participants screened and to confirm eligibility or record
 reasons for screening failure, as applicable.
- Procedures conducted as part of the participant's routine clinical management (eg, blood count) and obtained before signing of ICF may be utilized for screening or baseline purposes provided the procedure met the protocol-specified criteria and was performed within the time frame defined in the SoA (Section 2).
- The maximum amount of blood collected from each participant over the duration of the study, including any extra assessments that may be required, will not exceed 500 mL.
- Repeat or unscheduled samples may be taken for safety reasons or for technical issues with the samples.
- The following time window tolerances apply to all protocol assessments:

Predose	- 60 to 0 min (- 60 to -15 min for spirometry)
0h - 4h post	- 5 / + 10 min
5h – 24h post	- 20 / + 20 min

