9.2.1. Time Period and Frequency for Collecting AE and SAE Information

- All SAEs will be collected from the signing of the ICF until the follow-up visit at the time points specified in the SoA (Section 2). However, any SAEs assessed as related to study participation (e.g., study treatment, protocol-mandated procedures, invasive tests, or change in existing therapy) or related to a GSK product will be recorded from the time a subject consents to participate in the study.
- All AEs will be collected from the start of treatment until the follow-up visit at the time points specified in the SoA (Section 2).
- Medical occurrences that begin before the start of study treatment but after obtaining informed consent will be recorded on the Medical History/Current Medical Conditions section of the case report form (CRF) not the AE section.
- All SAEs will be recorded and reported to the sponsor or designee immediately and no later than in 24 h, as indicated in Appendix 4. The investigator will submit any updated SAE data to the sponsor within 24 h of it being available.
- Investigators are not obligated to actively seek AEs or SAEs in former study participants. However, if the investigator learns of any SAE, including a death, at any time after a participant has been discharged from the study, and he/she considers the event to be reasonably related to the study treatment or study participation, the investigator must promptly notify the sponsor.
- The method of recording, evaluating, and assessing causality of AEs and SAEs and the procedures for completing and transmitting SAE reports are provided in Appendix 4.

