9.2.4. Regulatory Reporting Requirements for SAEs

- Prompt notification by the investigator to the sponsor of a SAE is essential so that legal obligations and ethical responsibilities towards the safety of participants and the safety of a study treatment under clinical investigation are met.
- The sponsor has a legal responsibility to notify both the local regulatory authority and other regulatory agencies about the safety of a study treatment under clinical investigation. The sponsor will comply with country-specific regulatory requirements relating to safety reporting to the regulatory authority, Institutional Review Boards (IRB)/Independent Ethics Committees (IEC), and investigators.
- Investigator safety reports must be prepared for suspected unexpected serious adverse reactions according to local regulatory requirements and sponsor policy and forwarded to investigators as necessary.
- An investigator who receives an investigator safety report describing a SAE or other specific safety information eg, summary or listing of SAE) from the sponsor will review and then file it along with the Investigator's Brochure and will notify the IRB/IEC, if appropriate according to local requirements.

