12.3. Appendix 3: Study Governance Considerations

Regulatory and Ethical Considerations

- This study will be conducted in accordance with the protocol and with:
 - Consensus ethical principles derived from international guidelines including the Declaration of Helsinki and Council for International Organizations of Medical Sciences (CIOMS) International Ethical Guidelines
 - Applicable International conference on harmonization (ICH) Good Clinical Practice (GCP) Guidelines
 - Applicable laws and regulations
- The protocol, protocol amendments, ICF, Investigator Brochure, and other relevant documents (eg, advertisements) must be submitted to an IRB/IEC by the investigator and reviewed and approved by the IRB/IEC before the study is initiated.
- Any amendments to the protocol will require IEC/IRB approval before implementation of changes made to the study design, except for changes necessary to eliminate an immediate hazard to study participants.
- The investigator will be responsible for the following:
 - Providing written summaries of the status of the study to the IRB/IEC annually or more frequently in accordance with the requirements, policies, and procedures established by the IRB/EC
 - Notifying the IRB/IEC of SAE or other significant safety findings as required by IRB/IEC procedures
 - Providing oversight of the conduct of the study at the site and adherence to requirements of 21 CFR, ICH guidelines, the IRB/IEC, European regulation 536/2014 for clinical studies (if applicable), and all other applicable local regulations

Financial Disclosure

Investigators and sub-investigators will provide the sponsor with sufficient, accurate financial information as requested to allow the sponsor to submit complete and accurate financial certification or disclosure statements to the appropriate regulatory authorities. Investigators are responsible for providing information on financial interests during the course of the study and for 1 year after completion of the study.

Informed Consent Process

• The investigator or his/her representative will explain the nature of the study to the participant or his/her legally authorized representative and answer all questions regarding the study.

- Participants must be informed that their participation is voluntary. Participants
 or their legally authorized representative will be required to sign a statement of
 informed consent that meets the requirements of 21 CFR 50, local regulations,

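### One related death or life-threatening event other than anaphylaxis does not require dosing to stop in the other participants (Section 8.1.3)

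*Protocol*

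**What the plan says.** The current Section 8.1.3 has two tiers. The first concerns one person: "Dosing will be stopped for any individual participant in case of SAEs", and likewise for any adverse event that the investigator thinks might endanger that participant. The second concerns the whole study: "dosing will be stopped and the study will be put on halt if any of the below scenarios occurred". Restart then needs an internal safety review and an approved substantial amendment.

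Five scenarios trigger the second tier. Four require two or more participants within a dose level with related events of one category: grade 3 respiratory, grade 3 hematologic, severe hypersensitivity, and grade 3 heart rate or blood pressure. The fifth is the only one that a single participant can set off: "One (1) or more subjects receiving study treatment experience anaphylaxis that is deemed possibly or probably related to study drug by the investigator".

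Other sections add duties and powers around this rule. Section 9.2.1: "All SAEs will be recorded and reported to the sponsor or designee immediately and no later than in 24 h". Section 9.2.4: "Investigator safety reports must be prepared for suspected unexpected serious adverse reactions". Section 9 asks for immediate discussion of safety concerns with the sponsor "to determine if the participant should continue or discontinue study treatment". Under Section 8.2 a participant "may be withdrawn at any time at the discretion of the investigator for safety, behavioral, compliance or administrative reasons".

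**The concern.** Followed exactly, the rule makes one related anaphylaxis enough to halt the study and one related death from, for example, bronchospasm, arrhythmia or hemolysis not enough. Appendix 4 classes anaphylaxis as a grade 4 allergic reaction, so the protocol already accepts that one potentially life-threatening related event can justify a halt. It applies that principle to one event type only.

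The gap matters most in the repeat-dose cohorts (Part 1 Cohorts A and B, Part 2 Cohort B), where the other participants are partway through 14 days of twice-daily dosing. In Part 2 Cohort A, a single-dose cohort, it concerns only those not yet dosed. Section 3.1 states that this is the first administration of this formulation to humans. Section 3.3.1 reports lung deterioration and bronchospasm in COPD patients from the label of the aerosolized product, and deaths with lung pathology in rats given this formulation at 68.7 mg/kg; the rat no-effect level in Section 5.5 is 32.5 mg/kg. Whether the other participants are dosed again after such an event should not be left to discretion alone.

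**Working it through.** **Does any provision require the others to stop?** Assume one related SAE, fatal or life-threatening, not anaphylaxis.

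- 8.1.3, first tier: mandatory, but for the affected participant only. The word individual, followed by the second tier introduced as additional, rules out a study-wide reading.
- 8.1.3, second tier: 4 two-participant scenarios + 1 anaphylaxis scenario = 5. None is met by this event on its own.
- 8.1.1 and 8.1.2: liver and QTc rules for individual participants.
- 5.1 and 7.2: mandatory reviews before Part 1 Cohort B, Part 2 Cohort A and Part 2 Cohort B begin. They do not govern dosing inside a running cohort.
- 9: discussion with the sponsor about whether the participant continues.
- 9.2.1, 9.2.4 and Appendix 3: reporting to the sponsor, regulators, investigators and the ethics committee.
- 5.1 (dosing may be adjusted), 8.2 (withdrawal) and Appendix 3 (termination by the sponsor): all permissive. Appendix 3 also lifts the need for prior ethics approval of a design change, "except for changes necessary to eliminate an immediate hazard to study participants"; this allows urgent action but does not command it.

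No provision requires it.

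**Could the event complete a two-participant count?** Three of the four scenarios say grade 3. The vital-signs table in Appendix 4 defines a separate grade 4, labelled potentially life threatening. Literally, a grade 4 or fatal event is not a grade 3 event. If grade 3 is read as grade 3 or higher, the count is completed only when another participant at that dose level has already had a related event of the same category.

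**Who is affected?** Inputs are the cohort sizes in Sections 5.1 and 10.1, with the event on active drug.

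- Each Cohort B (12 active + 2 placebo = 14): 12 − 1 = 11 other active participants; 14 − 1 = 13 others in all.
- Part 1 Cohort A (6 active + 2 placebo = 8): 6 − 1 = 5 other active participants; 8 − 1 = 7 others in all.
- Planned course: 14 days × 2 = 28 doses each. The number still to come depends on the day of the event.

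**Timing.** Doses are about 12 h apart (Section 6.3.1) and the outer limit for SAE reporting is 24 h. Since 24 / 12 = 2, further scheduled doses can fall inside the reporting limit.

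**The case against.** The strongest reply is that nobody would carry on. Participants live in an accredited Phase I unit, SAEs are to be reported at once, safety concerns are to be discussed with the sponsor immediately, and both sponsor and investigator have the power to stop. The drug is ribavirin, approved at far higher doses; Table 1 puts predicted exposure at 60 mg twice daily 8-fold below oral ribavirin. Section 3.3.1 expects less acute lung risk from dry powder than from nebulised solution, and the earlier formulation was given to 48 healthy participants with no SAEs (Section 3.2). Appendix 8 also shows that Section 8.1.3 was revised in Amendment 1 after regulatory reviews.

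Most of this stands. The event may well be unlikely, a voluntary stop is likely, and the two-tier structure looks deliberate. None of it is a requirement to stop, and the amendment history does not show that the single-death case was considered.

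Three stronger readings are not supported:

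- A reader might infer that nothing happens beyond the affected participant. The reporting duties and between-cohort reviews are mandatory; what is missing is the stop of dosing.
- A reader might put the 5% rate from Section 10.1 into the triggers and quote a chance that no halt follows. That rate illustrates adverse outcomes in general. The documents give no rate for related fatal or life-threatening events.
- A reader might infer that even two deaths at a dose level would halt nothing. That follows only from the most literal reading of grade 3; the sensible intent is grade 3 or higher, but the text does not say so.

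**Conclusion.** The point holds as a statement about what the rule requires. After one related fatal or life-threatening SAE other than anaphylaxis, Section 8.1.3 mandates a stop for the affected participant only, and the rest of the protocol adds no mandatory stop for the others. The reach is at most 11 other active participants in a Cohort B and 5 in Part 1 Cohort A. These are upper bounds: they assume a full cohort with everyone else still on treatment and the event on active drug. The larger counts of 13 and 7 include placebo participants, and 28 doses is the whole planned course, not the exposure remaining.

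The conclusion rests on the wording, not on any event probability. The grade 3 wording is a second, smaller defect: it leaves unclear whether more severe events count at all. Both should be corrected, because the gap bears directly on participant safety and is cheap to close.

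**What to change.** Add a sixth scenario to the halt list in Section 8.1.3, built like the anaphylaxis line: *at least one participant on study treatment has a fatal or life-threatening SAE that the investigator judges possibly or probably related to study drug*. Keep it under the restart condition already stated there, and change grade 3 to grade 3 or higher in the respiratory, hematologic and vital-signs scenarios.

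It belongs in the existing list. A separate pause lifted by internal review alone would make restart easier after a related death than after one anaphylaxis or two grade 3 blood-pressure events. It would also give a life-threatening anaphylaxis two conflicting restart rules. Inside the list the two scenarios overlap harmlessly. Requiring a relation to study drug keeps out events attributed solely to bronchoscopy.

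The cost is one protocol amendment with ethics approval. The investigator judges causality blinded, so an event on placebo could halt the study, interrupt the 14-day course and disturb the lavage on days 10 to 13 or the exposure sampling on days 7 and 14. Section 7.4 already lets the sponsor's safety staff unblind any participant with an SAE, which can inform the review.

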- NOTE: An AE can therefore be any unfavorable and unintended sign (including an abnormal laboratory finding), symptom, or disease (new or exacerbated) temporally associated with the use of a study treatment.

Events Meeting the AE Definition

- Any abnormal laboratory test results (hematology, clinical chemistry, or urinalysis)
 or other safety assessments (eg, ECG, radiological scans, vital signs measurements),
 including those that worsen from baseline, considered clinically significant in the
 medical and scientific judgment of the investigator (ie, not related to progression of
 underlying disease).
- Exacerbation of a chronic or intermittent pre-existing condition including either an increase in frequency and/or intensity of the condition.
- New conditions detected or diagnosed after study treatment administration even though it may have been present before the start of the study.
- Signs, symptoms, or the clinical sequelae of a suspected drug-drug interaction.
- Signs, symptoms, or the clinical sequelae of a suspected overdose of either study treatment or a concomitant medication. Overdose per se will not be reported as an AE/SAE unless it is an intentional overdose taken with possible suicidal/self-harming intent. Such overdoses should be reported regardless of sequelae.

Events NOT Meeting the AE Definition

- Any clinically significant abnormal laboratory findings or other abnormal safety assessments which are associated with the underlying disease, unless judged by the investigator to be more severe than expected for the participant's condition.
- The disease/disorder being studied or expected progression, signs, or symptoms of the disease/disorder being studied, unless more severe than expected for the participant's condition.
- Medical or surgical procedure (eg, endoscopy, appendectomy): the condition that leads to the procedure is the AE.
- Situations in which an untoward medical occurrence did not occur (social and/or

convenience admission to a hospital).

• Anticipated day-to-day fluctuations of pre-existing disease(s) or condition(s) present or detected at the start of the study that do not worsen.

Guidance for Grading Adverse Events

Taken from the Food and Drug Administration (FDA) Toxicity Grading Scale for Healthy Adult and Adolescent Volunteers Enrolled in Preventive Vaccine Clinical Trials.

The purpose of this appendix is to provide guidance and it is to be used in conjunction with the investigator's judgment.

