Guidance for Grading Vital Signs Adverse Events

Vital Signs *	Mild (Grade 1)	Moderate (Grade 2)	Severe (Grade 3)	Potentially Life Threatening (Grade 4)
Fever (°C) ** (°F) *	38.0 – 38.4 100.4 – 101.1	38.5 – 38.9 101.2 – 102.0	39.0 – 40 102.1 – 104	> 40 > 104
Tachycardia - beats per minute	101 – 115	116 – 130	> 130	ER visit or hospitalization for arrhythmia
Bradycardia - beats per minute***	50 – 54	45 – 49	< 45	ER visit or hospitalization for arrhythmia
Hypertension (systolic) - mm Hg	141 – 150	151 – 155	> 155	ER visit or hospitalization for malignant hypertension
Hypertension (diastolic) - mm Hg	91 – 95	96 – 100	> 100	ER visit or hospitalization for malignant hypertension
Hypotension (systolic) – mm Hg	85 – 89	80 – 84	< 80	ER visit or hospitalization for hypotensive shock
Respiratory Rate – breaths per minute	17 – 20	21 – 25	> 25	Intubation

^{*} Participant should be at rest for all vital sign measurements

Allergic Reactions

Grade 1 allergic reaction (Pruritis without rash):

Participants with Grade 1 allergic reaction should be evaluated by the investigator immediately. The study drug should be permanently discontinued if the following signs or symptoms are noted at any time:

• Temperature >38.5°C

^{**} Oral temperature; no recent hot or cold beverages or smoking

^{***} When resting heart rate is between 60 - 100 beats per minute. Use clinical judgment when characterizing

- Eosinophilia
- · Respiratory involvement including brochospasm, laryngospasm, or angioedema
- Any indication of internal organ involvement (hepatitis, nephritis)

In the absence of the above signs or symptoms, participants with Grade 1 allergic reaction may continue the study drug at the discretion of the investigator. The participant should be advised to contact the investigator immediately if there is any worsening of the allergic reaction and/or if any systemic signs or symptoms worsen. If the allergic reaction is considered to be most likely due to concomitant illness or non-study medication, standard management, including discontinuation of the likely causative agent, should be undertaken. If no other causative factor is found after clinical evaluation, the participant may be treated symptomatically until the rash resolves. Antihistamines, topical corticosteroids or antipruritic agents may be prescribed. The participant should remain on the study to be followed for safety and PK.

Grade 2 allergic reaction (Localized urticaria):

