Participants with Grade 2 allergic reaction should be evaluated by the investigator immediately. The study drug should be permanently discontinued if the following signs or symptoms are noted at any time:

- Temperature >38.5°C
- · Eosinophilia
- Respiratory involvement including brochospasm, laryngospasm, or angioedema
- Any indication of internal organ involvement (hepatitis, nephritis)

In the absence of the above signs or symptoms, participants with Grade 2 allergic reaction may continue the study drug at the discretion of the investigator. The participant should be advised to contact the investigator immediately if there is any worsening of the allergic reaction and/or if any systemic signs or symptoms worsen. If the allergic reaction is considered to be most likely due to concomitant illness or non-study medication, standard management, including discontinuation of the likely causative agent, should be undertaken. If no other causative factor is found after clinical evaluation, the participant may be treated symptomatically until the rash resolves. Antihistamines, topical corticosteroids or antipruritic agents may be prescribed. The participant should remain on the study to be followed for safety and PK.

Grade 3 allergic reaction (Generalized urticaria or angioedema):

Participants will permanently discontinue the study medication and be withdrawn from the trial. Participants will be treated as clinically appropriate. Participants should be followed up until resolution of the adverse event and standard management should be undertaken.

Grade 4 allergic reaction (Anaphylaxis):

Participants will permanently discontinue the study medication and be withdrawn from the trial. Participants will be treated as clinically appropriate. Participants should be followed up until resolution of the adverse event and standard management should be undertaken.

Revised ACTG Toxicity	Definition	Investigator action
Grade		
Grade 1	Pruritus without rash	May continue therapy
Grade 2	Localized urticaria	May continue therapy
Grade 3	Generalized urticaria Angioedema	Discontinue therapy
Grade 4	Anaphylaxis	Discontinue therapy

Definition of SAE

If an event is not an AE per definition above, then it cannot be an SAE even if serious conditions are met (eg, hospitalization for signs/symptoms of the disease under study, death due to progression of disease).

A SAE is defined as any untoward medical occurrence that, at any dose:

a. Results in death

b. Is life-threatening

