- Congestive heart failure
- Arrhythmias
- Valvulopathy
- Pulmonary hypertension
- Cerebrovascular events/stroke and transient ischemic attack
- Peripheral arterial thromboembolism
- Deep venous thrombosis/pulmonary embolism
- Revascularization

Recording AE and SAE

AE and SAE Recording

- When an AE/SAE occurs, it is the responsibility of the investigator to review all documentation (eg, hospital progress notes, laboratory, and diagnostics reports) related to the event.
- The investigator will then record all relevant AE/SAE information in the CRF.
- It is **not** acceptable for the investigator to send photocopies of the participant's medical records to GSK in lieu of completion of the GSK /AE/SAE CRF page.
- There may be instances when copies of medical records for certain cases are

requested by GSK. In this case, all participant identifiers, with the exception of the participant number, will be redacted on the copies of the medical records before submission to GSK.

• The investigator will attempt to establish a diagnosis of the event based on signs, symptoms, and/or other clinical information. Whenever possible, the diagnosis (not the individual signs/symptoms) will be documented as the AE/SAE.

Assessment of Intensity

The investigator will make an assessment of intensity for each AE and SAE reported during the study and assign it to 1 of the following categories:

- Mild: An event that is easily tolerated by the participant, causing minimal discomfort and not interfering with everyday activities.
- Moderate: An event that causes sufficiently discomfort and interferes with normal everyday activities.
- Severe: An event that prevents normal everyday activities. An AE that is assessed as severe should not be confused with an SAE. Severe is a category utilized for rating the intensity of an event; and both AE and SAE can be assessed as severe.

An event is defined as 'serious' when it meets at least 1 of the predefined outcomes as described in the definition of an SAE, NOT when it is rated as severe.

Assessment of Causality

- The investigator is obligated to assess the relationship between study treatment and each occurrence of each AE/SAE.
- A "reasonable possibility" of a relationship conveys that there are facts, evidence, and/or arguments to suggest a causal relationship, rather than a relationship cannot be ruled out.
- The investigator will use clinical judgment to determine the relationship.

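### The hypersensitivity halt in Section 8.1.3 counts severe events, not Grade 3 events, so two related Grade 3 allergic reactions at one dose level need not stop the study

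*Protocol*

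**What the plan says.** Section 8.1.3 lists scenarios under which dosing stops and the study is put on hold. Restart needs an internal safety review and an approved substantial amendment, so these are mandatory rules.

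Four scenarios need at least two subjects within a dose level, with events judged possibly or probably related. The respiratory, hematologic and vital-signs rules all use grade 3; the hematologic one, for instance, applies when subjects "experience a grade 3 hematologic adverse event". The hypersensitivity rule uses another word: "Two (2) or more subjects, within a dose-level, receiving study treatment experience severe hypersensitivity related adverse event". A fifth scenario halts the study after a single related anaphylaxis.

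Appendix 4 (Section 12.4) holds two scales that bear on an allergic event:

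- **Intensity, for every event.** "The investigator will make an assessment of intensity for each AE and SAE reported during the study", as mild, moderate or severe. The top category is defined by function: "Severe: An event that prevents normal everyday activities".
- **Allergic grade, by clinical sign.** Grade 1 is pruritus without rash, Grade 2 localised urticaria, Grade 3 generalised urticaria or angioedema, and Grade 4 anaphylaxis. For Grade 3 the instruction is: "Participants will permanently discontinue the study medication and be withdrawn from the trial".

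The allergy text and table carry no mild, moderate or severe label. Severe and Grade 3 are equated in one place only, a column heading of the vital-signs grading table.

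**The concern.** A rule that halts a study automatically should have a trigger that everyone reads the same way. Here the trigger word has a formal definition in the protocol, and that definition is not the allergy grade. One scale records the effect on everyday activities and the other records which sign is present, so the two can disagree. Section 6.3.3 restricts participants to light activities such as reading or watching television. Generalised urticaria in such a setting could reasonably be rated moderate.

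What is at stake is the automatic study-level halt. Suppose two participants at one dose level have related Grade 3 allergic reactions, without anaphylaxis and without two qualifying respiratory events. Both leave the trial, but no other rule in Section 8.1.3 automatically stops dosing of the others. The repeat-dose cohorts are dosed twice daily for 14 days, so other participants may still be mid-course when the second reaction occurs.

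**Working it through.** The plan gives no figure to reproduce here. The check compares definitions and then counts.

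**Step 1: the qualifiers in Section 8.1.3**

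| Halt scenario | Subjects needed | Qualifier |
|---|---|---|
| Respiratory | 2 within a dose level | grade 3 |
| Hematologic | 2 within a dose level | grade 3 |
| Vital signs | 2 within a dose level | grade 3 |
| Hypersensitivity | 2 within a dose level | severe |
| Anaphylaxis | 1 | none |

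**Step 2: what the qualifier means for an allergic event.** Under the Appendix 4 intensity assessment, an event is severe only if it prevents everyday activities. Under the Appendix 4 allergy scale, a reaction is Grade 3 if it shows generalised urticaria or angioedema. Neither condition implies the other.

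**Step 3: the count.** Take two participants at one dose level, each with a related Grade 3 allergic reaction. Score 1 if the reaction is rated severe in intensity and 0 if not. The rule fires when the sum is at least 2.

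| First reaction | Second reaction | Count, rule as written | Halt? | Count if Grade 3 qualifies | Halt? |
|---|---|---|---|---|---|
| severe | severe | 1 + 1 = 2 | yes | 2 | yes |
| severe | not severe | 1 + 0 = 1 | no | 2 | yes |
| not severe | severe | 0 + 1 = 1 | no | 2 | yes |
| not severe | not severe | 0 + 0 = 0 | no | 2 | yes |

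The halt is reached in 1 of 4 rating pairs as written and in 4 of 4 if Grade 3 qualifies. The pairs are not equally likely, so this is not a probability.

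**Step 4: illustration under an assumption.** The protocol does not say how often a Grade 3 allergic reaction would be rated severe. Call that share q and assume independent ratings. Given two such reactions, the chance that both count is q². This is 0.75² = 0.5625 at q = 0.75, 0.5² = 0.25 at q = 0.5, and 0.25² = 0.0625 at q = 0.25. Only at q = 1 do the two readings agree.

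**Step 5: other provisions.**

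- The anaphylaxis halt covers Grade 4 only.
- The respiratory halt needs two related grade 3 respiratory events.
- The cohort reviews in Sections 5.1 and 7.2 govern progression to the next cohort.
- The immediate discussion with the sponsor in Section 9 concerns whether the individual continues treatment.
- The sponsor's right to terminate (Appendix 3) is discretionary.

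None of these automatically stops the remaining participants in the case described.

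**The case against.** The best counter-argument is that the intended meaning is fairly clear. The vital-signs table and the allergy grades both come under "Guidance for Grading Adverse Events" in Appendix 4, and that table equates severe with Grade 3. Anaphylaxis, as Grade 4, has its own halt, which leaves Grade 3 as the natural target of the two-subject rule. On that reading there is no gap. This is probably what was meant, but the rule does not say so, the equation is not repeated for allergy, and the formal definition of severe says something else.

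It can also be said that choosing a different qualifier is not an error: severe is a defined term, and any severity-based trigger depends on the rating. That is true. But the result is that two reactions serious enough to force permanent withdrawal may contribute nothing to the halt.

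There may even be a reason for the word. Sections 6.2.1 and 6.2.2 use severe hypersensitivity for Stevens-Johnson syndrome, toxic epidermal necrolysis and erythema multiforme, which are not on the allergy scale; a bare Grade 3 trigger could miss them. That is a good reason to keep the word severe in the rule, but not to leave Grade 3 out. It also gives the phrase a third possible sense.

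Finally, the consequences are largely contained. Grade 3 reactors are withdrawn. Any serious event, or any event the investigator thinks may endanger the participant, stops that person's dosing. Section 5.1 also lets dosing frequency and duration in the repeat-dose cohorts be adjusted on emerging safety data. All of this stands and limits the severity, but the measures that reach other participants are discretionary.

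**Conclusion.** The point holds and is minor. As written, the hypersensitivity halt can give a count of 2, 1 or 0 for the same two Grade 3 allergic reactions, and it reaches its threshold in only 1 of the 4 possible rating pairs. The conclusion rests on reading severe by its Appendix 4 intensity definition, and it matters only for related, non-anaphylactic Grade 3 reactions that no other halt catches. It assumes no event rates; the q² figures are illustrative. Confidence is moderate, because the authors probably meant Grade 3 and site staff may well apply the rule that way.

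**What to change.** In Section 8.1.3, replace the severe-event wording of the hypersensitivity scenario with: *hypersensitivity related adverse event that is an allergic reaction of Grade 3 or higher (Appendix 4) or is severe in intensity*. Appendix 4 needs no change.

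This keeps every event that the literal rule already counts, including severe reactions that are not on the allergy scale, and adds Grade 3 reactions whatever their intensity rating. Merely declaring that severe means Grade 3 would be shorter, but it could drop severe events that the allergy scale does not describe.

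The cost is one phrase, with no new data or visits. The downside is a halt that is triggered slightly more easily, with restart requiring a substantial amendment.
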